8.6 Trial specific preventive measures

All participants will receive standard supportive care established at the sites which may include off-label use of certain drugs that are deemed to be effective in COVID-19 (e.g. hydroxychloroquine,

lopinavir/ritonavir). In addition, escalation of treatment with off-label use of certain drugs (e.g. tocilizumab) in deteriorating participants is allowed during the trial. In terms of risk, conestat alfa, a recombinant human protein, has a very favourable side effect profile and major adverse events attributable to study medication are not expected in this study. Anaphylactic reactions are exceptionally rare and have only been observed in a single patient with a pre-existent allergy to rabbits. Although patients with rabbit allergy will be excluded from participating in the study, included subjects will be monitored for anaphylactic events during and at least for at least 12 hours after the last administration of conestat alfa. If patients develop type 1 allergic reactions following the administration of conestat alfa treatment according to in-house guidelines (potentially involving administration of antihistamines, corticosteroids, intravenous fluids and if needed adrenaline) will be provided.

No influence of conestat alfa on laboratory parameters or vital signs, including ECG was observed in previous clinical studies. Hence, we will not perform additional laboratory monitoring exceeding routine laboratory controls planned by the treating team (with the exception of the above mentioned additional biomarker analyses). No interactions with other drugs are known.

If female, patients must be/have: Post-menopausal, defined as the absence of menses for at least one year, OR Surgically sterile, defined as a bilateral tubal ligation at least 6 months prior to administration of study drug, bilateral oophorectomy, or complete hysterectomy, OR using an effective means of contraception with a failure rate less than 1% per year (e.g. oral contraceptives, contraceptive injections, intrauterine device, double-barrier method, male partner sterilization) OR a negative pregnancy test before study entry/randomisation. We expect the rate of female patients of childbearing age who may become pregnant to be <10% of all patients potentially eligible for this study. Due to the short treatment period (3 days) and half-life of conestat alfa (2.5 hours) an effective means of contraception is not mandatory after/during the treatment phase.

8.7 Concomitant Interventions (treatments)

All participants will receive standard supportive care established at the sites which may include off-label use of certain drugs that are deemed to be effective in COVID-19 (e.g. hydroxychloroquine, lopinavir/ritonavir, prophylactic anticoagulation). In addition, escalation of treatment with off-label use of certain drugs (e.g. tocilizumab) in deteriorating participants is allowed during the trial. Randomisation will be stratified by site to compensate for different standards of supportive care. Off-label use of drugs for the treatment of COVID-19 will be recorded in the eCRF. Escalation of treatment is one outcome of interest.

Patients are allowed to use all their regular medication during the trial. In addition, patients will receive all drugs required for the treatment of COVID-19 or its consequences. The care of the participant will remain unaffected by inclusion into the study or by study group assignment.

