Study Centre(s):	Multi-national study (it is planned to recruit patients in approximately 4-6 centers in Switzerland, Brazil and Mexico)
Statistical Considerations:	
Detailed methodology for statistical analyses of the data collected in this trial will be documented in a Statistical Analysis Plan.
 
Full Analysis Set/Intent-to-Treat Population: The FAS/ITT Population is defined as all patients who are randomly allocated to a study arm. Statistical analyses will be based on the treatment arm to which the patient was allocated.
 
Safety Population: The Safety Population is defined as all patients who received at least one dose of conestat alfa.
 
The primary endpoint WHO 7-point outcome scale at day 7 will be analyzed by nonparametric logrank test stratified by its baseline values with two-sided α-level of 5 %.
 
The secondary endpoint is time to improvement of at least 2 points. It will be tested only after a significant test of the primary endpoint (a priori ordered hypotheses), therefore, no alpha adjustment is necessary.
 
Furthermore, 95% confidence intervals will be determined, and the results will be presented graphically by means of box-and-whisker plots.
 
Time to event (e.g. death, virological clearance, defervescence) will be displayed by Kaplan-Meier plots and compared with a logrank test. Appropriate statistical tests will be used for the analysis of other outcomes of interest and will be detailed in the statistical analysis plan prior to unlocking of the study database.

GCP Statement:	This study will be conducted in compliance with the protocol, the current version of the Declaration of Helsinki, the ICH-GCP or ISO EN 14155 (as far as applicable) as well as all national legal and regulatory requirements.

ABBREVIATIONS

Provide a list of abbreviations used on the protocol - to be completed

AE	Adverse Event
BASEC	Business Administration System for Ethical Committees, (https://submissions.swissethics.ch/en/)
CA	Competent Authority (e.g. Swissmedic)
CEC	Competent Ethics Committee
CS	Complement system
C1INH	C1 esterase inhibitor
COVID-19	Coronavirus disease 2019
CRF	Case Report Form
ClinO	Ordinance on Clinical Trials in Human Research (in German: KlinV, in French: OClin, in Italian: OSRUm)
eCRF	Electronic Case Report Form
CTCAE	Common terminology criteria for adverse events
DSUR	Development safety update report
GCP	Good Clinical Practice
IB	Investigator's Brochure
Ho	Null hypothesis

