6.2.1 Randomisation

Participants will be randomized to two parallel groups in a 2:1 ratio in an open-label controlled design to receive either conestat alfa (intervention) in addition to standard of care (SOC) or SOC only (control). Randomisation will be stratified by the study site before inclusion using permuted-block randomization with varying block sizes. Allocation will be concealed, and randomization implemented via the electronic data capture system software SecuTrial®.

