11.4 Planned Analyses

11.4.1 Datasets to be analysed, analysis populations

A review of the database will be conducted in a blinded manner shortly before the database will be locked, and any decisions made at that meeting (blinded Data Review Meeting) concerning the statistical analysis, e.g., additional outcomes and populations, pooling of sites for efficacy analysis, will be documented in the Statistical Analysis Plan (SAP).

Missing data for the primary endpoint will be imputed by means of the Last-observation-carried-forward (LOCF) method.

Safety Population: The Safety Population is defined as all patients who received at least one dose of conestat alfa. Statistical analyses will be based on the actual treatment the patient received.

Full Analysis Set/Intent-to-Treat Population: The FAS/ITT Population is defined as all patients who are randomly allocated to a study arm. Statistical analyses will be based on the treatment arm to which the patient was allocated.

For quantitative data, the number of patients with non-missing information, means, medians, standard

deviations and extremes will be determined. For qualitative data, absolute and relative frequencies will be calculated. Moreover, changes from baseline (V2, d0) will be calculated.

Per Protocol Population: The PP Population is defined as all patients in the FAS/ITT Population who complete the study and who do not have any major protocol violations, including the following:

- Patients who had major inclusion/exclusion criteria violations.

Sufficient compliance is expected because of IV administration of the IMP.

The PP Population will be determined by a blinded review in the Data Review Meeting (DRM) of the data prior to database lock.

The primary efficacy analysis will be based on the FAS/ITT Population in this superiority trial; an additional efficacy analysis will be performed on the PP Population. The Safety Population will be used for all safety analyses.

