11.4.2 Primary Analysis

The primary endpoint WHO 7-point outcome scale at day 7 will be analyzed by nonparametric logrank test stratified by its baseline values with two-sided α -level of 5 %.

Two adaptive interim analyses after 40 and 80 patients are planned according to the Pocock adjusted levels $\alpha_p = 0.0221$. The results of the sequential groups are combined by the inverse-normal-method (Lehmacher, Wassmer, 1999). There are no prespecified futility margins, but the DSMB can stop the study in the case of insufficient interim results.

Furthermore, 95% confidence intervals will be determined, and the results will be presented graphically by means of box-and-whisker plots.

The analyses will be carried out by the trial biostatistician.

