11.4.3 Secondary Analyses

The secondary endpoints are time to improvement of at least 2 points on the WHO 7-point outcome scale, the proportion of subjects with an ALI (defined by PaO₂/FiO₂ ratio of <300mmHg) within 14 days after enrolment and the proportion of participants alive and not having required invasive or non-invasive ventilation at 14 days after enrolment. They will be tested only after a significant test of the primary endpoint (a priori ordered hypotheses), therefore, no alpha adjustment is necessary.

Quantitative secondary study parameters will be described based on their mean, standard deviation, median, IQR, minimums and maximums and portrayed by Kaplan-Meier plots and compared with the logrank test.

Qualitative secondary study parameters will be analyzed by means of absolute and relative frequencies. Pairwise Chi-Square tests will be carried out in order to compare each of the active treatments to placebo. Moreover, 95% confidence intervals for the treatment differences will be calculated.

Other outcomes of interest will be analyzed by means of descriptive and exploratory statistics.

The analyses will be carried out by the trial biostatistician.

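### Randomisation is stratified by site, but the stated efficacy tests leave site out; to the extent that sites differ, the analysis is conservative and gives up a little power

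*Protocol*

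**What the plan says.** Section 6.2.1: "Randomisation will be stratified by the study site before inclusion using permuted-block randomization with varying block sizes". No other stratification factor is named. Section 8.7 gives the reason: "Randomisation will be stratified by site to compensate for different standards of supportive care". The synopsis says that "it is planned to recruit patients in approximately 4-6 centers in Switzerland, Brazil and Mexico", and both arms receive standard of care under local guidelines.

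Under Section 11.4.2 the day-7 score "will be analyzed by nonparametric logrank test stratified by its baseline values". For the binary secondary endpoints, Section 11.4.3 says: "Pairwise Chi-Square tests will be carried out in order to compare each of the active treatments to placebo", followed by "Moreover, 95% confidence intervals for the treatment differences will be calculated". Time to improvement is compared by a logrank test with no stratum named.

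Site appears in the analysis text only in Section 11.4.1. There, pooling of sites for efficacy is one of the decisions that may be taken at the data review meeting shortly before database lock and then recorded in the SAP.

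**The concern.** The protocol's reason for stratifying by site is that care differs between sites, so it treats site as likely to affect outcome. Blocking by site removes between-site variation from the treatment comparison. A test that ignores site still counts that variation as noise, so its standard error is larger than the true one. Intervals are then wider than they need to be, and some power is lost in a trial of 120 patients.

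Timing matters too. Both interim tests (after 40 and 80 patients) precede the data review meeting, and stage results are combined by the inverse-normal method. A decision on site taken at that meeting comes too late for stages already tested.

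Separately, the chi-square sentence describes a trial with several active arms and a placebo. This trial has one active arm, and Section 3.6 says that a placebo group is omitted.

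**Working it through.** **Inputs from the protocol.** Effect 1 point, SD 1.5, two-sided 5%, power 80%, 2 x 38 for a fixed design, 120 = 80 + 40 in total (Section 11.2); Pocock level 0.0221 with looks at 40, 80 and the end (Section 11.4.4); 15-20% of patients progressing to ventilation (Section 3.8).

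**Assumed.** R, the share of score variance lying between sites: 0, 5, 10 and 20%.

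**The plan's own figure.** n per arm = 2 x (1.960 + 0.842)^2 x 1.5^2 / 1^2 = 35.3, rounded up to 36. Dividing by the Wilcoxon efficiency 0.955 gives 37.7, so 2 x 38 reproduces. Three looks at 0.0221 give a simulated overall error of 4.98%, so the Pocock level reproduces as well.

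**Effect of ignoring site on the primary test.** With allocation blocked by site, the true variance of the treatment difference is (1 - R) times the variance an unadjusted test assumes. The standard error is therefore too wide by the factor 1/sqrt(1 - R): for example, 1/sqrt(0.90) = 1.054. The overall error and power below were simulated for the three-look Pocock test with 2:1 allocation, efficiency 0.955 and standardised effect 1/1.5 = 0.67.

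| R | SE too wide by | Overall type I error, unadjusted | Power, unadjusted | Power, adjusted | Difference (points) |
|---|---|---|---|---|---|
| 0% | 0% | 5.0% | 88.0% | 88.0% | 0 |
| 5% | 2.6% | 4.3% | 88.4% | 89.6% | 1.2 |
| 10% | 5.4% | 3.7% | 88.9% | 91.2% | 2.2 |
| 20% | 11.8% | 2.5% | 90.0% | 94.1% | 4.1 |

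Unadjusted power rises with R because the total SD is held at 1.5, so a larger site share leaves less true variance within sites.

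**How site is added matters.** These are fixed-sample simulations at two-sided 5%: 120 patients, five sites of 20-30, baseline scores 3 to 5, effect 0.85 points, Monte Carlo error about 1 point. The columns run over R = 0 / 5 / 10 / 20%.

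| Analysis | Power, baseline only | Power, baseline and site |
|---|---|---|
| Rank-based covariate adjustment | 75.7 / 77.2 / 78.5 / 79.6% | 75.6 / 78.0 / 80.6 / 84.0% |
| Logrank, strata crossed baseline x site | 72.9 / 74.7 / 76.3 / 76.9% | 68.7 / 71.8 / 73.1 / 78.0% |

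Crossing three baseline scores with five sites makes 15 cells, or 40/15 = 2.7 patients per cell in a stage of 40. Coarser strata do not solve this. A van Elteren test over baseline (3 versus 4 or more) by three countries, in stages of 40, gave 66.9 / 70.7 / 72.4 / 76.5%, against 71.9 / 73.7 / 74.1 / 75.5% for baseline alone.

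**Binary secondary endpoints.** Control rate 20% (top of the range in Section 3.8), five sites, log odds ratio -1.5, and assumed site spread 0 / 0.5 / 1.0 on the logit SD scale. Chi-square power was 69.2 / 70.2 / 68.1%, against 69.3 / 70.7 / 70.9% for a site-stratified Cochran-Mantel-Haenszel test. Chi-square type I error was 5.2 / 4.7 / 3.9%. A gap of about 8 points (59.0 versus 67.1%) appeared only with an assumed 30% control rate and an extreme spread of 1.5.

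**The case against.** The sentence in Section 8.7 is not wrong in itself. Stratified allocation balances the arms within site, which is what it claims, and it promises no site-adjusted test. A reader might infer that leaving site out biases the comparison or makes the test invalid. It does neither, since any error is on the conservative side. This stands.

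A reader might also infer that power is certainly lost. That depends on a between-site variance the documents do not give, and with no site differences the loss is zero. Because the primary test already stratifies by baseline score, differences in case mix between sites are partly absorbed. Only the residual site share counts, so a given raw site share overstates the loss. At the planned effect, simulated power stays above the 80% target throughout, with or without site. All of this stands and limits the point.

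Finally, the synopsis leaves detailed methods to the SAP, which is not shown, and the mention of pooling suggests that site was considered. This carries some weight for the secondary endpoints. For the primary endpoint it carries less, because the protocol itself fixes the test and its stratifier, and the one stated occasion for deciding on sites falls after both interim tests.

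**Conclusion.** The mismatch between design and stated analysis is real, and its cost is small and conditional. For residual between-site shares of 5 to 20%, the standard error is 2.6 to 11.8% too wide and the power forgone at the planned effect is about 1 to 4 points. At a share of zero nothing is lost. For the binary endpoints at a 20% control rate the loss is 0 to about 3 points. Type I error is at or below nominal, apart from simulation error.

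These sizes rest on assumed site variances, a Wilcoxon-type approximation to the primary test and simulated site patterns. They do not show that the trial is underpowered. The change is worth making because it costs almost nothing and aligns the analysis with the randomisation. The wording error in the chi-square sentence does not depend on any of these assumptions.

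**What to change.** Before the first interim analysis, specify the following.

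- **Primary endpoint:** site enters as a covariate beside baseline score, with small sites pooled by country under a rule fixed in advance. A rank-based covariate adjustment stays closest to the planned nonparametric test; a proportional-odds model with baseline score and site or country is an alternative. Do not use fully crossed baseline x site or baseline x country strata. Apply the same analysis at every stage.
- **Binary secondary endpoints:** Cochran-Mantel-Haenszel tests and stratified risk differences with their intervals, by site or pooled country.
- **Time to improvement:** a logrank test stratified by site or pooled country.
- **Section 11.4.3:** replace the reference to several active treatments and placebo with *conestat alfa plus SOC versus SOC*.

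The cost is a few sentences and a few lines of code. Site is already recorded at randomisation, and no new data are needed.

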8.8 Study Drug / Medical Device Accountability

The in-house Pharmacy will be responsible for maintaining accurate drug storage and dispensing logs including records about shipments to the trial sites, return to the Sponsor and document on-site destruction if applicable. Drugs will be stored at each study site in accordance with GCP and GMP requirements and will be inaccessible to unauthorized personnel. Lot/batch numbers will be recorded. All unused and used conestat alfa vials will be retained at the site until drug inventory has been completed by the Monitor.

The ward nurses will use study drugs only within the framework of this clinical study and in accordance with this protocol. Receipt, distribution, return, and destruction (if any) of study drugs will be properly documented. Accountability records will include dates, quantities, batch/serial numbers, expiration dates, and patient numbers and sign off by the pharmacist or nurse. These records will adequately document that the patients were provided the doses as specified in the protocol and should allow reconciliation activities from Monitor for all conestat alfa received from the Sponsor.

The drug accountability process will be described in further detail separately in the Monitoring Manual.

8.9 Return or Destruction of Study Drug / Medical Device

Any study product that remains unused at the termination of the study will be returned to the Sponsor (Basel) or destroyed in accordance with institutional policies and this process will be recorded.

9. STUDY ASSESSMENTS

9.1 Study flow chart(s) / table of study procedures and assessments

Study Periods	Screening	Intervention Period				Follow-up	
		1	2	3	4	5	6
Visit	1	2	3	4	5	6	7
Time (weeks or days, or hours)	d-1 to d0 ¹	d0	d1	d2	d3-13 during admission*	d14 (+/-2d) or discharge	wk4 (+/-5d)
In- /Exclusion Criteria	x						
Patient Information and Informed Consent	x						
Randomisation	x						
Demographics		x					
Medical History and Physical Examination		x				x	
Vital Signs including Respiratory Rate ⁹		x	x	x	x	x	
Laboratory Tests (blood)		x	x		x ³	x	
Virology testing		x ²			x ²	x ²	
Administer Study Medication ⁴		x	x	x	x		
Assessment of WHO ordinal scale		x	x	x	x	x	x
Assessment of ICU admission and/or mechanical ventilation		x	x	x	x	x	x
Laboratory assessment in detail:							
Routine full blood count		x ⁵	x		x ³	x	
Routine coagulation studies		x ⁵	x		x ³	x	
Routine biochemistry including LDH		x ⁵	x		x ³	x	
Serum pregnancy test	x ⁶						
Ferritin, IL-6, D-Dimer		x ⁵	x ¹¹		x ³	x	
C1INH concentration ⁷		x	x			x	
Additional samples in Basel ¹⁰ :		x					
Complement proteins (e.g. C4d, C5a)		x	x		x ³	x	
Inflammatory cytokines (e.g. IL-10)		x	x		x ³	x	
Contact activation and coagulation proteins (e.g. factor XII)		x	x		x ³		
C1INH concentration and activity		x ⁸	x ⁸		x (d3, 7, 10)	x	
Urinary markers of renal injury		x	x		x ³	x	
Blood volume (ml), total/study specific (Basel ¹⁰)	5/5 (5)	12/12 (22)	12/12 (22)		12/5 (10)	12/12 (17)	
Urine volume (ml), study specific in Basel ¹⁰		5	5		5	5	
(Serious) Adverse Events		x	x	x	x	x	x

¹Eligibility criteria have to be assessed within 72 hours after hospital admission. Randomisation may occur on the day of hospital admission.

²Monitoring of SARS-CoV-2 viral load will be performed in Basel and optional in other centers. This will include performance of a quantitative SARS-CoV-2 PCR from upper or lower respiratory tract at baseline

and subsequently once between day 4-7 (according to local standard) and again on day 14 if participants are still admitted or between day 10-13 if discharged earlier. Standard operating procedures include the performance of a second swab following a first negative swab.

³Routine laboratory tests will be performed on days 3, 5, 7, and 10 during hospital admission according to standard procedures of the study site, but will include a set of hematology, coagulation and biochemistry parameters. Additional blood samples will be collected at the same time.

⁴IMP will be administered during a 64 hour period (+/-4 hours). Trial medication will be stopped in participants that are discharged or transferred to another facility.

⁵Can be omitted if results are available from the same day.

⁶A pregnancy test will be performed in women who may become pregnant, are sexually active, and do not use adequate contraceptive measures.

⁷Collection of samples will be before 1st administration of study medication and subsequently at least 4 hours after the administration of study medication.

⁸Collection of samples will be before 1st administration, 10 (+/-5) minutes after the 1st administration (day 0) and before and 10 (+/-5) minutes after one administration on day 1.

⁹The worst value recorded on a given day will be documented.

¹⁰optional for other centers depending on their ability to collect, centrifuge, aliquot and store blood and urine samples at -80°C.

¹¹IL-6 will not be measured on day 1

* If the patient was already discharged before day 7, the assessment of the WHO ordinal scale will be conducted via a short telephone interview (Score 1 or 2).

9.2 Assessments of outcomes

9.2.1 Assessment of primary outcome

For the analysis of the primary endpoint, illness severity will be assessed on each day after enrolment (worst status) with the use of the WHO Ordinal Scale for Clinical Improvement (score 0 will be omitted and score 6 and 7 will be combined) and the score on day 7 will be analysed stratified by its baseline value.

Patient State	Descriptor	Score
Uninfected	No clinical or virological evidence of infection	0
Ambulatory	No limitation of activities	1
	Limitation of activities	2
Hospitalized Mild disease	Hospitalized, no oxygen therapy	3
	Oxygen by mask or nasal prongs	4
Hospitalized Severe Disease	Non-invasive ventilation or high-flow oxygen	5
	Intubation and mechanical ventilation	6
	Ventilation + additional organ support – pressors, RRT, ECMO	7
Dead	Death	8

Figure 4: WHO ordinal scale for clinical improvement. For the current study, score 0 will be omitted, and score 6 and 7 will be combined.

The worst score on a given day (between 0:00 and 24:00 hours) will be used for the categorization

Patient State	Description	Score
---------------	-------------	-------

Outpatient	No limitation in activities	1
	Limitation in activities	2
Hospitalized Mild disease	No oxygen therapy	3
	Oxygen by mask or nasal prongs	4
Hospitalized Severe disease	Non-invasive ventilation or high-flow oxygen	5
	Intubation, mechanical ventilation +/- additional organ support	6
Death	Death	7

